4.1. Primary Objective(s) or Main Objective(s)

This study is exploratory in nature and there are no specified hypotheses or performance requirements for the Primary Objectives. All mentions of the intervention in the objectives below refer to the process improvement intervention that will be implemented at the start of Phase II. All mentions of the diagnosis of SND refer to symptomatic SND.

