4.1.1.1. Endpoint Definition

The absolute change in the proportion of subjects diagnosed with SND at pre-specified time points (% = number diagnosed/number enrolled x 100 at time point t where t = 6, 12, and any additional 6-month interval for which there is sufficient follow-up information) and the absolute change in the number of subjects diagnosed with SND per person-year. An SND diagnosis will be determined by the response on the Diagnosis Form on the CRF. If any response under the heading of Sinus Node Dysfunction is selected, the subject will be considered to have been diagnosed with SND. Responses under the heading of Sinus Node Dysfunction include

- Minimally symptomatic SND, with heart rate less than 40 bpm while awake and no evidence of chronotropic incompetence (Class IIb)
- SND, with heart rate less than 40 bpm and no symptom rhythm correlation present (Class IIa)
- Symptomatic bradycardia, brady-tachy syndrome (Class I)
- Symptomatic bradycardia, sinus arrest/pause/exit block (Class I)
- Symptomatic bradycardia, sinus brady (Class I)
- Symptomatic Chronotropic incompetence (Class I)
- Symptomatic SND/bradycardia, drug induced (Class I)
- Symptomatic SND, sinus tachycardia (Class I)
- Syncope, spontaneous or induced in EP study (Class I)
- Syncope of unknown origin with EP findings (Class IIa)

If none of these diagnoses were indicated on the Diagnosis Form on the CRF, the subject will be considered to not have been diagnosed with SND.

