4.2.5.1. Endpoint Definition

Compare the difference in QOL and functional status between pre-implant and 6 months post-implant. The composite physical and mental scores from Version 2 of the SF-12 Health Survey will be used to assess QOL.

[REDACTED]

[REDACTED] [REDACTED]

[REDACTED]

[REDACTED]

[REDACTED]

[REDACTED] [REDACTED]

[REDACTED]

This document is electronically controlled. Printed copies are considered uncontrolled.

Confidential

[REDACTED]

[REDACTED]

[REDACTED]

[REDACTED]

[REDACTED]

[REDACTED]

5. Investigation Plan

Study Design Overview

The study may be conducted in countries located in Central and Eastern Europe (CEE), Greater China, India, Latin America, Asia, and Middle East and Africa (MEA). Countries from other geographies may be added in the future. The distribution of centers will be approximately 10 per geography or country and is determined by local evidence needs.

Approximately 1,650 subjects per geography/country, or up to 14,850 subjects worldwide, will be enrolled in the study. An enrollment target of 6 subjects per center per month is desired to make center-specific outcomes more meaningful and reliable in measuring changes in diagnostic rates and patient acceptance of indicated therapy. Centers that enroll faster than others will be allowed to enroll until 20% of the sample size for the geography/country has been reached for a maximum of 330 subjects per site - 110 maximum in Phase I and 220 maximum in Phase II.

All study subjects will be followed until the study exit criteria are met or until official study closure. Study closure is defined as closure of a clinical study that occurs when Medtronic and/or regulatory requirements have been satisfied per the Clinical Investigation Plan and/or by a decision by Medtronic or regulatory authority, whichever occurs first. The expected study duration per geography/country, from first enrollment to last follow-up, is approximately 4.5 years per geography/country.

Subjects will have successfully completed the study if one of the following criteria has been met:

1. Subject does not meet a class I or class II SND indication for pacing therapy
2. Subject meets an indication for pacing but not an SND indication for pacing therapy
3. Subject has met an SND indication for pacing therapy and did not receive a market released pacemaker from the Medtronic family of devices
4. Subject has met an SND indication for pacing therapy but will not be receiving pacing therapy

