8.2. General Methodology

8.2.1. Special Considerations

The study will have an enrollment restriction. The maximum number of subjects to be enrolled at any given study center is 20% of the expected sample size in that geography; 20% of 1650 subjects equals 330 subjects per study center.

Sample size calculations will account for an attrition rate in the study of 10%.

An analysis will be built to examine temporal confounding. Since the study design does not randomize the treatment and control subjects it is possible that the time elapsed over Phase I and Phase II of the study will confound the results. To examine the possibility of temporal confounding, an interrupted time series regression analysis will be performed. This analysis will adapt Rubin's causal model for rate parameters.

This document is electronically controlled. Printed copies are considered uncontrolled.

Confidential

Rubin's causal model for linear outcome Y is $Y = \beta_0 + \beta_1 X + \beta_2 D$, where X is time and D is a dummy variable for group assignment, before and after intervention. To adopt this model for rate parameters estimated in the primary objectives of the study, the model to be fit is $\log(Y) = \beta_0 + \beta_1 X + \beta_2 D + \log(Z)$ where Y is a binary response to indicate an SND diagnosis and Z is the amount of subject follow-up. The same model will also be fit to model the rate of IPG treatment. If an association is seen by testing β_1 , then temporal confounding exists.

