8.4. General Summaries

The Medtronic statistician who is assigned to the project will conduct all statistical analysis. Sample size package PASS 2008 was used for sample size evaluation. The two primary endpoints are the change in the proportion of subjects with an SND diagnosis after intervention and the change in the proportion of subjects receiving IPG therapy after intervention. In current practice, both of these proportions are unknown for a set of subjects meeting the study inclusion criteria. Three principles will guide the statistical analysis outlined below. The first principle is that the sample size calculations will use exact confidence intervals and tests to compare binomial proportions. The second principle of the analysis is that sample size calculations for Phase II of the study design will depend on the outcomes observed in Phase I of the study design. Due to this, the Phase II sample size calculations provided herein are preliminary calculations that will be amended once Phase I data collection is completed. In general the study will start with a 1:2 collection ratio for Phase I and Phase II sample sizes. Twice as many subjects are enrolled in Phase II of the study design so that the study may also examine any temporal drift in the outcomes of interest or subject demographics. The third principle of the analysis is that both the

This document is electronically controlled. Printed copies are considered uncontrolled.

Confidential

statistical methods and the sample size calculations will be geography specific because the study outcomes are expected to vary by geography.

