8.5.1.1. Analysis Methods

A. Statistical Methodology

To compare the proportion of subjects with an SND diagnosis pre-intervention (Phase I) to the proportion post-intervention (Phase II), a chi-square test will determine statistical significance. The proportion of subjects diagnosed will be evaluated at multiple time points because the time to diagnosis is expected to vary by geography. Thus, times are pre-specified starting at 6 months and any additional 6-month interval thereafter for which there is sufficient follow-up data available to compare study phases.

Proportions calculated at all available time points will be reported. Additionally a Poisson regression will compare the average number of subjects with an SND diagnosis in Phase I and Phase II where the subject time in study is treated as an offset in the model. The above described tests will be performed only for subjects in the South Asia geographical region as per section 6.

[REDACTED]

[REDACTED]

This document is electronically controlled. Printed copies are considered uncontrolled.

Confidential

[REDACTED]

[REDACTED]

[REDACTED]

B. Determination of Patients/Data for Analysis

All subjects that are enrolled in the study will be included in the determination of the proportion estimates. The proportion estimates will be calculated based on information from fixed time points at 6 months of follow-up, 12 months of follow-up, and any additional 6-month interval thereafter for which there is sufficient follow-up data available to compare study phases. The number of subjects that obtain an SND diagnosis by pre-specified time point $t = 6, 12, \text{ etc.}$, is included in the numerator and the number of subjects enrolled is included in the denominator.

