8.5.1.2. Sample Size Methods and Assumptions

The proportion of SND diagnoses in bradycardia subjects is currently unknown within the study geographies. The PANARM HF study of 2000 subjects found that 146 out of 331 bradycardia subjects (44%) had symptomatic SND and that 15 (10%) of SND subjects opted for IPG therapy (internal data on file). The power calculations conservatively assume that the SND diagnosis will be 20% at six months of follow-up, or equivalently an SND incidence of 0.4 diagnoses per person-year. Thus, the margin of error will be $\pm 4\%$ in a sample of 500 subjects per geography/country, based on a 95% confidence interval. If 500 subjects are collected in Phase I and 1000 subjects are collected in Phase II, assuming a type I error of 0.05 and power of 0.90, a chi-square test will detect an increase in SND diagnosis of at least 8%. For example, the study will find a statistically significant difference between a Phase I SND percentage of 20% at 6 months and a Phase II SND percentage of 28% at 6 months. The Poisson regression for the same scenario has a power of 0.95 to compare SND incidence of 0.4 versus 0.56 diagnoses per person-year. If the proportion of SND diagnoses is smaller than 20%, there will be more power to detect significant differences in the diagnosis proportion. Thus, the Phase II sample size will be recalculated within geography/country once Phase I data collection is complete. It is expected that the study attrition rate may be 10-15% of the study population. To account for attrition, *the sample size for Phase I will be 550 subjects per geography/country and for Phase II may be 1100 subjects per geography/country.*

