8.5.2.1. Analysis Methods

A. Statistical Methodology

To compare the proportion of subjects that receive indicated therapy pre-intervention (Phase I) to the proportion post-intervention (Phase II), a Fisher's Exact test will determine statistical significance. A Fisher's exact test is recommended for smaller sample sizes. The proportion of subjects diagnosed will be evaluated at multiple time points because the time from diagnosis to implant is expected to vary by geography. Shorter time intervals will be used to evaluate the proportion of implants than for the proportion of diagnosis because time from diagnosis to implant is typically shorter than the time from enrollment to SND diagnosis. Thus, times are pre-specified starting at 3 months and any additional 3-month interval thereafter for which there is sufficient follow-up data available to compare study phases. Proportions calculated at all available time points will be reported. Additionally, a Poisson regression will compare the average number of subjects with an implant where the subject time in study beginning at the time of SND diagnosis is treated as an offset in the model. The above described tests will be performed only for the South Asia geography as described in Section 6. Further, similar tests will compare the differences in the types of therapy received in Phase I and Phase II. For example, a Fisher's exact test will compare the frequency of dual chamber device use pre- and post-intervention.

This document is electronically controlled. Printed copies are considered uncontrolled.

Confidential

B. Determination of Patients/Data for Analysis

Subjects that meet inclusion criteria and obtain an SND diagnosis shall be included in this analysis. The proportion estimates will be calculated based on information from fixed time points at 3 months of follow-up, 6 months of follow-up, and any additional 3-month interval thereafter for which there is sufficient follow-up data available to compare study phases. The number of subjects that obtain an IPG by pre-specified time point $t = 3, 6, \text{ etc.}$, will be included in the numerator and the number of subjects with an SND diagnosis will be included in the denominator.

C. Additional Analyses

- In addition to the overall diagnosis and treatment rates between Phase I and Phase II, various descriptive summaries of the subjects will be explored by geography, including the following:

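### The Poisson and interrupted time series models, as visibly written, offset a once-only event by total time in study, so the per-person-year ratio is not an incidence rate ratio

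*SAP*

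**What the plan says.** SAP 4.1.1.1 defines the first primary endpoint as a change in proportions at fixed times together with "the absolute change in the number of subjects diagnosed with SND per person-year". SAP 4.1.2.1 does the same for implants.

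Three models estimate or examine these rates:

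- **Diagnosis (SAP 8.5.1.1):** Poisson regression "where the subject time in study is treated as an offset in the model".
- **Implant (SAP 8.5.2.1):** Poisson regression in which "the subject time in study beginning at the time of SND diagnosis is treated as an offset in the model". A start is given but no end.
- **Temporal confounding (SAP 8.2.1):** a log-linear model with a binary response and offset log(Z), where "Z is the amount of subject follow-up".

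Protocol 11.1 states the same rule for both Poisson models, with no redaction beside it. In planning, SAP 8.5.1.2 treats 20% diagnosed at six months as "or equivalently an SND incidence of 0.4 diagnoses per person-year".

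**The concern.** An incidence rate divides first events by the time during which a first event could still occur. Under the visible wording, a subject diagnosed at month 1 and followed to month 12 contributes twelve months instead of one.

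This would matter less if post-event time were alike in the two phases, but the documents make it differ:

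- Protocol 4.3 plans about 12 months of enrollment in Phase I and 18 in Phase II. Phase I subjects all leave 6 months after the last enrollment.
- Only Phase II has a six-month post-implant visit (Protocol 5.6).
- SAP Section 5 introduces outcome-dependent completion rules with "Subjects will have successfully completed the study if one of the following criteria has been met". They cover subjects without an SND indication and indicated subjects who will not be paced.

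The ratio then mixes the intervention effect with how long each phase keeps people after the event. In one fixed window it reduces to a risk ratio, which the chi-square and Fisher tests already address. Over unequal follow-up it is neither a risk ratio nor a rate ratio. The check for temporal confounding, important in a non-randomized before–after design, has the same flaw.

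**Working it through.** **1. The plan's own rates.** From SAP 8.5.1.2, 20% and 28% at six months give 0.20/0.5 = 0.40 and 0.28/0.5 = 0.56 per person-year. These match the SAP exactly, and they count six full months for every subject, including those already diagnosed. This is only weak evidence of intent. The implant figure of 0.25 for 10% at three months (SAP 8.5.2.2) fits neither total time (0.10/0.25 = 0.40) nor time at risk (−ln 0.90/0.25 = 0.42).

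**2. Equal follow-up, constant hazard, planned effect.**
- Diagnosis at risk: −ln(0.80)/0.5 = 0.446 and −ln(0.72)/0.5 = 0.657, ratio 1.47. Written: 0.56/0.40 = 1.40. Simulated power (500/1000 subjects, two-sided Wald test at 0.05) is 0.87 written and 0.93 at risk. The SAP states 0.95.
- Implant at risk, 10% against 26% at three months: ln(0.74)/ln(0.90) = 2.86. Written: 0.26/0.10 = 2.60 at three months, and (1 − 0.74²)/(1 − 0.90²) = 0.4524/0.19 = 2.38 at six. Simulated three-month power (100/200 subjects) is 0.88–0.89 written and 0.92–0.93 at risk.

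**3. Everyone kept to phase closure.** Follow-up is uniform on 0.5–1.5 years (Phase I) and 0.5–2 years (Phase II), with means 1 and 1.25.
- Phase I: [1 − (0.80 − 0.80³)/0.4463]/1 = 0.355.
- Phase II, planned effect: [1 − (0.72 − 0.72⁴)/(0.6570 × 1.5)]/1.25 = 0.434. The ratio is 1.22 against 1.47, with power about 0.70 against above 0.99.
- Phase II, no effect: [1 − (0.80 − 0.80⁴)/(0.4463 × 1.5)]/1.25 = 0.333. The ratio is 0.94 against 1.00, with about 5% rejections for both.

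**4. Completion criteria applied (assumed retention).** Exponential work-up has mean 1.8, 3 or 6 months and ends in SND with probability 0.20 or 0.28. Time to the treatment decision has mean 1 or 2 months. Implant probability is 0.10 or 0.26. Non-SND and unpaced subjects leave 1 week, 1 month or 3 months after the decision. Implanted subjects stay to closure in Phase I and to the six-month visit in Phase II.

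| Case | Written | At risk |
|---|---|---|
| Diagnosis, planned effect | 1.20–1.36 | 1.39–1.41 (clock stops at a non-SND decision); 1.40–1.49 (clock runs to exit) |
| Diagnosis, no effect | 0.98–1.03 | 0.99–1.01 |
| Implant, planned effect | about 1.9–2.5 | about 2.6–3.0 |
| Implant, no effect | 0.97–1.18 | 0.94–1.03 |

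In the middle case (3, 1 and 1 months), diagnosis power is 0.64 written against 0.82 (stop at decision) or 0.87 (run to exit). Implant power is 0.71–0.74 against about 0.91. With no effect the written models reject in 1–4% (diagnosis) and 0–2% (implant) of trials.

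**5. Direction.** With accrual as in step 3, no effect, and subjects leaving 6 months (Phase I) or 1 month (Phase II) after diagnosis, the written diagnosis ratio is 1.14. With 1 and 6 months it is 0.87. The at-risk ratio is 1.00 in both.

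**6. Zero time.** Protocol 5.3 lets a patient enroll at any time the criteria are met, so a diagnosis may fall on or before enrollment. Suppose this holds for 10% of 100 Phase I diagnoses and 30% of 280 in Phase II (assumed shares). Then log(0) drops 10 and 84 events. Over six months, mean time to the remaining diagnoses is 0.241 and 0.236 years. Person-years are 400 × 0.5 + 90 × 0.241 = 221.7 and 720 × 0.5 + 196 × 0.236 = 406.3. With events dropped the ratio is (196/406.3)/(90/221.7) = 1.19. With them kept at a token time it is about (280/406.3)/(100/221.7) = 1.53. With no effect the pair is 0.80 and 1.02.

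**The case against.** **The time variable may be defined out of sight.** Redacted blocks follow the sentence in SAP 8.5.1.1, and the SAP's version table mentions SAS code that is not visible. Time in study could be shorthand for time to event. This stands as a limit: the point concerns the visible rule. It is not removed, because Protocol 11.1 and SAP 8.2.1 say the same without adjacent redaction.

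**The analysis carries little weight.** SAP 8.4 says "The two primary endpoints are the change in the proportion of subjects with an SND diagnosis after intervention" and the corresponding change for IPG therapy. The Poisson model is introduced as an addition. SAP 4.1 says "This study is exploratory in nature and there are no specified hypotheses or performance requirements for the Primary Objectives". The log-rank tests (8.5.4.1, 8.5.5.1) already handle time at risk. All true, and the reason the point is minor. Even so, the per-person-year change is in both endpoint definitions, and the log-rank test does not estimate it.

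**The sizes rest on assumed behavior.** Keeping everyone to closure ignores the completion criteria. It also stretches the hazard to 1 − 0.72⁴ = 73% diagnosed by month 24, so step 3 is a bound and not a forecast. The lags in steps 4 and 5 and the shares in step 6 are not in the documents, and for non-implanting sites Protocol 5.3 expects enrollment before the final diagnosis. Zero time is mainly a consequence of the corrected offset, not a present error. Step 6 shows only why the fix needs a rule.

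**Dilution dominates.** Every planned-effect result in steps 2 to 4 is below its at-risk value. Upward movement needs longer post-event retention in Phase I than in Phase II. It is material in step 4 only for implants with no effect.

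**Conclusion.** The concern holds as a minor point. Followed as visibly written, the offset counts time after a once-only event, so the reported ratio is not an incidence rate ratio. This does not depend on the retention assumptions; only the size does.

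At the planned effect and equal six-month follow-up, the diagnosis loss is small (1.40 against 1.47). Under the completion criteria it is larger, and for implants it is substantial (about 1.9–2.5 against 2.6–3.0). The ratio can move either way, but the expected cost is dilution and lost power. The completion-criteria patterns give no excess of false positives. The fixed-time proportion tests and the log-rank tests are not affected.

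**What to change.** - **SAP 8.5.1.1:** run the offset from enrollment to the earliest of SND diagnosis, exit or closure of diagnostic data collection. Say which date ends the clock when a final non-SND diagnosis precedes exit.
- **SAP 8.5.2.1:** run it from SND diagnosis to the earliest of implant, exit or closure of implant data collection.
- **SAP 8.2.1:** use the same Z for each outcome.
- **Zero or negative time:** state a rule, for example half a day or one day, and report the number of such events by phase.
- **Sensitivity analysis:** carry subjects who exited as not indicated or not to be paced forward as event-free to the common closure date.
- If redacted text already defines time this way, say so in these sections.

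The cost is a sentence in each of the three sections, one rule, one sensitivity run and a re-derived time variable under the level I validation that SAP Section 9 already requires. Enrollment, diagnosis and implant dates are already needed for Secondary Objectives #2 and #3, so no new data are required.

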5.7 Study Exit

Subjects may be exited from the study for any of the following situations, including but not limited to:

- Subject does not meet an indication for pacing therapy
- Subject meets an indication for pacing but not a SND indication for pacing therapy
- Subject has met a SND indication for pacing therapy and did not receive a market released pacemaker from the Medtronic family of devices
- Subject has met a SND indication for pacing therapy but will not be receiving pacing therapy
- Subject has completed the final scheduled follow-up visit.

- Geography/country completion of Phase I follow-up
- Study Closure
- Subject lost to follow-up
- Subject death
- Subject did not meet inclusion/exclusion criteria
- Subject chooses to withdraw (e.g., consent withdrawal, relocation to another geographic location)
- Investigator deems withdrawal necessary (e.g., medically justified, failure of subject to maintain adequate study compliance)

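### The Poisson offset for both primary endpoints is time in study, which depends on the subject's outcome and on the phase, so the rate test can reject in either direction when equal shares are diagnosed or implanted

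*SAP*

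**What the plan says.** - **Endpoint.** SAP 4.1.1.1 defines the first primary endpoint as a change in proportion together with "the absolute change in the number of subjects diagnosed with SND per person-year". SAP 4.1.2.1 has the same two-part form for implants.
- **Offset.** For diagnosis, SAP 8.5.1.1 specifies a Poisson regression "where the subject time in study is treated as an offset in the model". For implants, SAP 8.5.2.1 specifies one "where the subject time in study beginning at the time of SND diagnosis is treated as an offset in the model". The readable text sets no fixed window for either offset and does not say whether it stops at the event.
- **What ends time in study.** SAP Section 5 states: "Subjects will have successfully completed the study if one of the following criteria has been met". The list includes "Subject does not meet a class I or class II SND indication for pacing therapy" and "Subject has met an SND indication for pacing therapy but will not be receiving pacing therapy". Protocol 5.7 is permissive: "Subjects may be exited from the study for any of the following situations, including but not limited to". Its list includes "Subject meets an indication for pacing but not a SND indication for pacing therapy".
- **Other ends.** Under Protocol 4.3, Phase I enrols for about 12 months and closes 6 months after the last enrolment. Phase II enrols for about 18 months; undiagnosed subjects leave 6 months after the last enrolment, and unimplanted subjects 6 months after the last diagnosis. Protocol 5.6 adds a visit 6 months after implant, in Phase II only.
- **Planning conversion.** SAP 8.5.1.2 equates 20% diagnosed at six months with 0.4 diagnoses per person-year, and sets 28% beside 0.56.

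**The concern.** A person-year denominator should measure the opportunity for the event. Here a negative outcome can itself stop the clock. A subject ruled out at two months contributes two months; one with no recorded decision contributes time to the end of the phase, which is later on average in Phase II. The diagnostic algorithms and patient education could change how quickly subjects are ruled out or decline. Post-implant follow-up can add Phase II time that has no Phase I counterpart.

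The rate half of each primary endpoint can then move although the same share is diagnosed or implanted, and it can disagree with the chi-square or Fisher test on the same data. The SAP does not say how such a disagreement would be read. The temporal-confounding model in SAP 8.2.1 also uses follow-up as its offset, so it does not remove the problem.

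**Working it through.** **1. The plan's own conversion.** 0.20 / 0.5 year = 0.40 and 0.28 / 0.5 year = 0.56. Both figures reproduce, but only if every subject, including those ruled out early, contributes a full 0.5 year. The specified offset does not ensure that. (Two separate matters, not used here: the stated Poisson power of 0.95 for 0.4 versus 0.56 does not reproduce with 0.5 year each, at 0.80 to 0.85 two-sided; and 10% at three months is 0.10 / 0.25 = 0.40 per person-year, not the stated 0.25.)

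**2. How little time is needed.** Hold 20% diagnosed in both phases and Phase I at 6 months per subject. Phase II reaches 0.56, the plan's whole target effect, when its mean time falls to 0.20 / 0.56 = 0.357 year, or 4.3 months.

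Suppose 60% of Phase II subjects are ruled out at 4 months (assumed):
- mean time = 0.4 × 0.5 + 0.6 × 4/12 = 0.40 year
- rate = 0.20 / 0.40 = 0.50; ratio = 0.50 / 0.40 = 1.25
- with 100 and 200 diagnoses (20% of 500 and 1000), SE of the log ratio = √(1/100 + 1/200) = 0.1225
- z = ln(1.25) / 0.1225 = 1.82, so two-sided rejection is about 45%.

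**3. Windows as the protocol sets them.** Assume uniform enrolment. Mean time to the end of the phase is 12/2 + 6 = 12 months in Phase I and 18/2 + 6 = 15 months in Phase II. Assume 20% SND in both phases, mean diagnosis time of 3 months, time stopped at diagnosis, and negatives exiting at mean 3 months (Phase I) or 2 months (Phase II), except a share s who stay to the end. Ignoring truncation, mean person-months are 0.2 × 3 + 0.8 × [(1 − s) × exit time + s × end time]:

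| s | Phase I | Phase II | Ratio (I/II months) | Simulated ratio |
|---|---|---|---|---|
| 0 | 0.6 + 0.8 × 3 = 3.0 | 0.6 + 0.8 × 2 = 2.2 | 1.36 | 1.35 |
| 25% | 0.6 + 0.8 × 5.25 = 4.8 | 0.6 + 0.8 × 5.25 = 4.8 | 1.00 | 1.00 |
| 50% | 0.6 + 0.8 × 7.5 = 6.6 | 0.6 + 0.8 × 8.5 = 7.4 | 0.89 | 0.90 |

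The share diagnosed is the same in every row; the ratio moves to either side of 1. If person-time is instead capped at 6 months with s = 0, the simulated ratio is about 1.28 with 47% rejection, while tests of the proportion reject about 5%.

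**4. Implant endpoint.** Assume 10% implanted in both phases, 100 and 200 SND subjects and a 6-month cap. Decliners exiting at mean 2 versus 1 month give a ratio of about 1.83 (30% rejection); 3 versus 1 month gives 2.46 (62%). If instead the offset runs on through the Phase II post-implant visit, with an assumed mean decline time of 3 months in Phase I, the ratio is 0.82 with no change in speed, 0.97 with declines 25% faster and 1.22 with declines 50% faster.

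**5. Two candidate remedies.** Crediting negatives to the end of their own phase, with identical decision times, gives (0.6 + 0.8 × 12) / (0.6 + 0.8 × 15) = 10.2 / 12.6 = 0.81; simulation gives 0.82 with 38 to 39% false rejection. With the SAP's 10 and 20 months of enrolment, simulation gives 0.71 and 75%. A fixed 6-month window in both phases gives 1.01 and 5.6%.

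**The case against.** **Exit is not automatic.** Protocol 5.7 only permits it, and the documents give no exit timings. In a simulation with equal windows and a mean decision time of 4 months, decisions 25% or 50% faster give ratios of only 1.05 or 1.11 (8% or 14% rejection) if half of the negatives never get a decision. This stands: the size cannot be fixed from the documents.

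**The direction is open.** A reader might infer that quicker negative decisions inflate the Phase II rate and so favour the intervention. The documents do not support that as a net result. Shorter time for negatives raises the rate, but the longer Phase II window and the Phase II-only follow-up lower it.

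**The rate test is secondary in weight.** The chi-square and Fisher tests decide significance, SAP 8.4 describes the primary endpoints as changes in proportions, and SAP 4.1 calls the study exploratory. The proportions keep all enrolled, or all SND, subjects in the denominator, so this mechanism does not touch them. That limits the consequence, but the rate remains part of both endpoint definitions.

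**Redaction.** Text after the Poisson paragraph in SAP 8.5.1.1 is blacked out, and the change log mentions SAS code that cannot be read. The offset may be defined there.

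**Some movement is real.** Earlier positive diagnoses also raise the rate and may be a genuine benefit. The distortion is the part that comes from negatives and from unequal windows.

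**Conclusion.** The concern holds as a distortion of uncertain sign. As readable, the offset lets person-time depend on outcome and on phase, and it is inconsistent with the SAP's own conversion to 0.4 per person-year. With equal shares diagnosed, the diagnosis rate ratio runs from about 0.9 to 1.35 as the share of negatives staying to the end of the phase goes from 50% to none. This rests on assumed exponential decision times, uniform enrolment and the planned 500 and 1000 subjects. The phase comparison is now confined to South Asia (SAP Section 6), whose actual numbers and exit timings the documents do not give. The point should be settled before the rate analyses are run; it does not affect the chi-square or Fisher tests.

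**What to change.** Define the offset in SAP 8.5.1.1 and 8.5.2.1, identically for both phases:

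- Count events and person-time only within one fixed window, for example 6 months from enrolment for diagnosis and 6 months from diagnosis for implant.
- Stop person-time at the event, death, withdrawal or loss to follow-up.
- Credit the full window to subjects exited as not indicated, not SND or not receiving pacing.
- Do not use the administrative end of each phase as the window, because the phases differ in length (working, step 5).
- For implants, a Phase I subject diagnosed late may reach phase closure before 6 months from diagnosis. State that person-time then stops at closure for everyone, decliners included.
- Use the same definition for the follow-up term in the SAP 8.2.1 model.

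The cost is SAP wording and one derived variable. No visit or exit rule changes. The rates become materially lower: in the 6-month scenario they fall from about 0.80 and 1.02 to about 0.39 per person-year, roughly half or less. They will also largely track the fixed-time proportions, so the Poisson result adds less independent information.
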